## **6.2 Dosing Modifications**

### **6.2.1 Overview**

Dose modifications for hematologic and non-hematologic toxicities are summarized in sections 6.2.2 and 6.2.3 respectively. Participants who have treatment delayed for greater than four weeks should discontinue protocol therapy.

A maximum of 2 dose reductions of carfilzomib or Dex and 1 dose reduction of PLD will be allowed for each participant. More than two dose reductions of Dex or one dose reduction of PLD will require the agent be discontinued. Participants that permanently discontinue Dex or PLD due to toxicity can remain on study and receive the other planned study drug doses at the investigator's discretion. Participants requiring a third dose reduction of carfilzomib will have treatment discontinued.

If the participant tolerates the reduced dose for one cycle, the participant may be dose escalated to the study drug dose(s) prior to reduction at the discretion of the Investigator.

Dose modifications should be followed directly for Cycle 1 for all patients treated in the phase I portion of the study. In Cycles 2+ for patients treated in the phase I portion, and for any cycle for patients treated in the phase II portion, dose modifications and delays different from those stated in the protocol for management of toxicities will be permitted at the discretion of the Principal Investigator.

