### 5.2 Phase I

Part 1- A phase I dose escalation of carfilzomib and PLD will be performed using a standard 3 + 3 design with a maximum of 4 dose levels (24 participants). The carfilzomib dose will be determined using a modified Fibonacci dose escalation, with a goal of three participants at each dose level.

Dose Level	Carfilzomib (mg/m  ) IV	PLD (mg/m  ) IV
-2	20	20
-1	20 on D1 and D2* 27 starting on D8	20
0 (Start)	20 on D1 and D2* 27 starting on D8	30
1	20 on D1 and D2* 36 starting on D8	30
2	20 on D1 and D2* 45 starting on D8	30
3	20 on D1 and D2* 56 starting on D8	30

\*- Please note that the D1 and D2 carfilzomib dose of 20mg/m^2 will only occur during Cycle 1. For all subsequent cycles, patients will receive the same dose of carfilzomib throughout at what is noted in this table to be the D8 dose.

Part 2- After the MTD of carfilzomib in combination with PLD has been determined, dose escalation will resume at the MTD of carfilzomib and PLD with the addition of dexamethasone. A maximum of 12 participants eligible for Maximal Tolerated Dose (MTD) analysis will be enrolled.

Dose Level	Carfilzomib (mg/m  ) IV	PLD (mg/m  ) IV	Dex (mg) IV or PO
-1	1 dose level below the MTD	1 dose level below the MTD	20
0 (Start)	MTD	MTD	20

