### 5.2.1 Dose Escalation Rule

Number of Participants with a DLT at a Dose Level	Escalation Decision Rule
0	Enter 3 participants at the next dose level.
1 out of 3	Enter 3 more participants at this dose level.  If none of the additional participants experiences a DLT, then proceed to the next dose level. If $\geq 1$ of the additional participants experiences a DLT, then dose escalation is stopped and the level below is declared the MTD.
$\geq 2$	Dose escalation is stopped. Enter 3 more participants at the next lower dose level if only 3 participants had previously been treated at that dose level.

Only after the last participant on at each dose level completes one cycle of treatment will the first participant in the next dose level be enrolled.

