### 5.2.2 Definition of Maximum Tolerated Dose

The maximum tolerated dose (MTD) is defined as the dose level immediately below the dose level at which 2 participants of a cohort (of 2 to 6 participants) experience dose limiting toxicity (DLT) during the first cycle of treatment. (See Section 6.0 for information on what constitutes a DLT.) Dose escalation will proceed until the MTD has been reached.

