#### 6.2.2.2 Neutropenia

Only neutropenia determined to be related to one or both study drugs require dose reductions or adjustments as described in this section. Colony-stimulating factor support (such as G-CSF or GM-CSF) for neutropenia is permissible at the discretion of the treating physician, but should not be given prophylactically. Participants who have treatment delayed for greater than four weeks should discontinue protocol therapy.

Dose modifications for neutropenia should be instituted as follows:

Grade	ANC	Modification
4	< 500	
First episode: Hold therapy until ANC resolves to grade <math>\leq 1</math> or baseline, then reduce carfilzomib by one dose level
 
Second episode: Hold therapy until ANC resolves to grade <math>\leq 1</math> or baseline, then further reduce carfilzomib by one more dose level and reduce PLD by one dose level
 
Third episode: Discontinue protocol therapy.

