### **8.0 DURATION OF THERAPY**

#### **8.1 Criteria for Removal from Study**

Treatment may continue until disease progression or clinical relapse, as defined in Sections 9.8 and 9.9 respectively, or until one or more of the following criterion applies:

- Participant withdraws consent
- Holding study drug(s) > 2 continuous weeks for adverse event(s)
- Adverse event(s) that, in the judgment of the Investigator, may cause severe or permanent harm or which rule out continuation of study drug.
- General or specific changes in the participant's condition render the participant unacceptable for further treatment in the judgment of the investigator
- Suspected or confirmed pregnancy
- Major violation of the study protocol
- Participant lost to follow-up
- The PI decides to remove the participant from study for any reason
- Death
- The treating center decides to close the study

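### Section 6.2.1 sets no MTD cap on re-escalation, so a phase I participant reduced for toxicity, even a Cycle 1 DLT, may return to a dose level the trial has rejected

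*Combined protocol and SAP*

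**What the plan says.** **Re-escalation (Section 6.2.1).** If a reduced dose is tolerated for one cycle, "the participant may be dose escalated to the study drug dose(s) prior to reduction at the discretion of the Investigator". One tolerated cycle and the Investigator's discretion are the only conditions. The next paragraph requires the modification rules to be followed directly in Cycle 1 of phase I. For phase I Cycles 2 onward, "dose modifications and delays different from those stated in the protocol for management of toxicities will be permitted" at the Principal Investigator's discretion.

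**Rejecting a level (Sections 5.2.1 and 5.2.2).** If a further DLT occurs in an expanded cohort, "then dose escalation is stopped and the level below is declared the MTD". The MTD is defined as "the dose level immediately below the dose level at which 2 participants of a cohort" have a first-cycle DLT. These rules govern cohort enrolment and the MTD declaration. They do not address participants already on treatment.

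**What happens after a hematologic DLT (Sections 6.1 and 6.2.2).** Grade 4 thrombocytopenia, grade 4 neutropenia and febrile neutropenia of grade 3 or higher are all DLTs. At the first episode of each, therapy is held and carfilzomib then drops one level. For neutropenia, for example, the hold lasts until recovery to grade 1 or less "or baseline, then reduce carfilzomib by one dose level". The participant stays on protocol therapy.

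**Limits on holds.** Section 6.2.1 states: "Participants who have treatment delayed for greater than four weeks should discontinue protocol therapy". Section 8.1 sets a shorter limit, under which holding drug for an adverse event for more than two continuous weeks is a removal criterion.

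**The concern.** Phase I exists to find the level above which this combination should not be given. A participant who had a DLT at a level, was reduced, and then tolerated the lower dose may be put back on the higher one. Nothing in Section 6.2.1 asks whether the higher level has been declared above the MTD in the meantime. For the participant whose DLT was the second in the cohort, the rejection has already happened by the time a return is possible, and it happened partly because of that participant's own toxicity.

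This is a patient-safety gap in a permission that the protocol states outright. It does not affect the statistical decision rule.

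**Working it through.** The plan gives no figure on this point. The check has three steps: trace the rules, size the dose step, and see in which cycles the step matters.

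**1. Can the situation arise?**
- A hematologic DLT leads to a one-level carfilzomib reduction, not removal (6.1, 6.2.2).
- DLTs are counted in Cycle 1 only (6.1). Return needs one tolerated cycle at the reduced dose. With 28-day cycles (7.1.4), the earliest return is Day 2 × 28 + 1 = 57, which is Cycle 3 Day 1, and later if there was a hold.
- The second DLT in the cohort rejects the level. For that participant the level is therefore already rejected by Day 57.
- The participant with the first DLT may differ. Accrual is about one per month (5.5) and a cohort may reach six, so that person could be re-escalated before the level is rejected.
- Sections 5.1 to 5.3, 6.1 to 6.2.3, 7.1.4, 8.1 and 14.0 contain no MTD cap on individual re-escalation. The monthly phase I data review in 14.0 sets no dose limit.

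**2. Size per dose.** Doses are from the Section 5.2 table. The MTD is taken as the level immediately below the rejected one. Excess = rejected dose ÷ MTD dose − 1.

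| Rejected level | Carfilzomib, rejected vs MTD (mg/m²) | Difference | Excess per dose |
|---|---|---|---|
| 1 | 36 vs 27 | 9 | 36/27 − 1 = 33% |
| 2 | 45 vs 36 | 9 | 45/36 − 1 = 25% |
| 3 | 56 vs 45 | 11 | 56/45 − 1 = 24% |
| 0 | 27 vs 27 | 0 | none |

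Levels 0 and −1 carry the same carfilzomib entry, "20 on D1 and D2* 27 starting on D8", so returning carfilzomib to 27 is no excess. Only PLD can exceed the MTD there (30 vs 20; 30/20 − 1 = 50%), and only if PLD was the drug reduced.

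**3. Size per cycle.** The current schedule has six carfilzomib doses per cycle through Cycle 6 and four from Cycle 7 (5.1). The comparator is the twice-weekly MTD regimen at six full doses.

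| Rejected level | MTD regimen, 6 doses | Rejected level, 6 doses | Rejected level, 4 doses |
|---|---|---|---|
| 1 | 6 × 27 = 162 | 6 × 36 = 216 | 4 × 36 = 144 |
| 2 | 6 × 36 = 216 | 6 × 45 = 270 | 4 × 45 = 180 |
| 3 | 6 × 45 = 270 | 6 × 56 = 336 | 4 × 56 = 224 |

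(mg/m² of carfilzomib per cycle.) With six doses, the rejected level exceeds the MTD regimen by 54, 54 and 66 mg/m². With four weekly doses it falls below that regimen at every level.

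If Cycle 2 is the tolerated reduced cycle, the per-cycle excess is confined to Cycles 3 to 6 on the current schedule, a ceiling of 4 × 6 = 24 doses. Participants on the schedule used before amendment 1 go weekly from Cycle 3. They would receive up to 4 × 4 = 16 doses in Cycles 3 to 6 that are higher dose by dose, but less per cycle than the twice-weekly MTD regimen.

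**The case against.** The best defence is that the plan deliberately separates the two questions. The MTD comes from first-cycle DLTs, and Section 6.1 sends later toxicity to the modification rules. Dosing after Cycle 1 then follows the individual's own tolerance, and the permission says only that a participant may be re-escalated. The route is also guarded:

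- Cytopenias must recover to grade 1 or baseline.
- A full reduced cycle must be tolerated.
- Blood counts are reviewed before carfilzomib dosing (7.1.4).
- A second hematologic episode cuts carfilzomib again and PLD as well, and a third ends therapy.
- The two-week criterion in 8.1 may remove some participants before any return.

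Much of this stands, and it keeps the reach small. It does not supply the missing limit. None of these safeguards refers to the MTD, the repeat-episode rules act only after further serious toxicity, and neither hold limit applies to a hold of two weeks or less.

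It is also fair to say that the Cycles 2 onward clause concerns managing toxicity, so it does not clearly cover re-escalating someone who is tolerating treatment. The gap does not depend on that clause. The clause simply contains no cap either.

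Four stronger readings are tempting, and the documents do not support them:

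- **Harmful excess until progression.** From Cycle 7, carfilzomib is weekly and PLD has stopped, so carfilzomib per cycle is below the twice-weekly MTD regimen.
- **Every rejected level creates at least two such cases.** Return is discretionary, and the first DLT participant may return before rejection.
- **Every DLT opens this route.** Under 6.2.3, grade 3 or higher infection resumes at full dose, and stomatitis and hand-foot reactions (PPE) affect PLD, not the carfilzomib dose.
- **A biased MTD.** Toxicity after Cycle 1 does not count toward it.

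**Conclusion.** The gap is real and worth closing. Section 6.2.1 permits return to the dose given before reduction with no limit if that level has been rejected, and no other section provides one. The clear case is a Cycle 1 hematologic DLT at carfilzomib level 1, 2 or 3, followed by a hold of two weeks or less and a tolerated reduced cycle.

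The size is 33%, 25% or 24% more carfilzomib per dose than the MTD at levels 1, 2 and 3, and no carfilzomib excess at level 0. The per-cycle excess over the twice-weekly MTD regimen is limited to Cycles 3 to 6 on the current schedule. These are dose steps, not estimates of risk. They assume that the MTD is the level immediately below and that Cycle 2 is the tolerated reduced cycle.

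The number affected is small and may be zero. Participants who were never dose-reduced and remain at a level later rejected are outside this point.

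**What to change.** Add to Section 6.2.1:

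> In phase I, a participant whose dose was reduced for toxicity may not be re-escalated to a dose level declared above the MTD for the regimen being received (with or without dexamethasone 20 mg); a participant already re-escalated to a level that is later declared above the MTD returns to the MTD from the next dose. This limit also applies to modifications made at the Principal Investigator's discretion in Cycles 2+.

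The cap is tied to the regimen because phase I determines two MTDs (2.1) and a Part 1 participant may add dexamethasone after Cycle 2 (7.3.4). A cap tied to the part of enrolment would miss that person if Part 2 rejected the same doses with dexamethasone. The step-down clause covers a participant re-escalated before the cohort's second DLT.

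The cost is two sentences and slightly less flexibility for individual participants. Re-escalation up to the MTD stays available, and no sample size or decision rule changes.

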### **6.2.2 Dosing Modifications for Hematologic Toxicities**

#### **6.2.2.1 Thrombocytopenia**

Only thrombocytopenia determined to be related to one or both study

drugs require dose reductions or adjustments as described in this section. Platelet transfusion support is permissible at the discretion of the treating physician. Participants who have treatment delayed for greater than four weeks should discontinue protocol therapy.

Dose modifications for thrombocytopenia should be instituted as follows:

Grade	Platelet	Modification
4	< 25,000	
First episode: Hold therapy until platelets resolve to grade <math>\leq 1</math> or baseline, then reduce carfilzomib by one dose level
 
Second episode: Hold therapy until platelets resolve to grade <math>\leq 1</math> or baseline, then further reduce carfilzomib by one more dose level and reduce PLD by one dose level
 
Third episode: Discontinue protocol therapy.

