
Stomatitis  Painful erythema, edema, or ulcers, but can eat
 
Painful erythema, edema, or ulcers, and cannot eat
	
2
 
3
	
First episode: Hold all drugs until resolved to <math>\leq</math> grade 1 then resume at the same dose.
 
Second episode: Hold all drugs until resolved to <math>\leq</math> grade 1 then resume carfilzomib at the same dose and PLD at 20 mg/m^2.
 
Third episode: Hold all drugs until resolved to <math>\leq</math> grade 1 then discontinue PLD and resume carfilzomib at the same dose.
 
First episode: Hold all drugs until resolved to <math>\leq</math> grade 1 then resume carfilzomib at the same dose and PLD at 20 mg/m^2.
 
Second episode: Hold all drugs until resolved to <math>\leq</math> grade 1 then discontinue PLD and resume carfilzomib at the

Requires parenteral or enteral support	4	same dose. Hold all drugs until resolved to $\leq$ grade 1, then discontinue PLD and resume carfilzomib at the same dose.
Tumor lysis syndrome, defined as $\geq 3$ of following:  $\geq 50\%$ increase in creatinine $\geq 50\%$ increase in uric acid $\geq 50\%$ increase in phosphorus $\geq 30\%$ increase in potassium $\geq 20\%$ decrease in calcium $\geq 2$ -fold increase in LDH	Any	Hold all drugs until all abnormalities in serum chemistries have resolved to baseline, then resume treatment at full doses.
Other non-hematologic toxicity	$\geq 3$	Hold suspected study drug(s) until toxicity resolves to $<$ grade 1 or baseline, then reduce suspected drug(s) by one dose level.

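### Section 6.2 does not define a one-level dose reduction, and from the starting level only one lower carfilzomib dose exists for the two reductions it orders

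*Combined protocol and SAP*

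**What the plan says.** Section 6.2.1 sets the limits: "A maximum of 2 dose reductions of carfilzomib or Dex and 1 dose reduction of PLD will be allowed for each participant". A third carfilzomib reduction ends treatment. Going beyond the limit for PLD or dexamethasone ends that agent.

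Sections 6.2.2.1 to 6.2.2.3 use both carfilzomib reductions. After a first qualifying episode therapy is held, "then reduce carfilzomib by one dose level". After a second the instruction is to "further reduce carfilzomib by one more dose level and reduce PLD by one dose level". A third ends protocol therapy. Several rows of Section 6.2.3 also reduce a drug by one level. The stomatitis rows instead name the dose: "then resume carfilzomib at the same dose and PLD at 20 mg"/m².

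The only numbered dose levels are the paired rows of the Section 5.2 table. Level 0 (the start) and level -1 carry the same carfilzomib entry, "20 on D1 and D2* 27 starting on D8", and differ only in PLD (30 and 20 mg/m²). Levels 1 and 2 are "20 on D1 and D2* 36 starting on D8" and "20 on D1 and D2* 45 starting on D8". Level 3 goes to 56, and level -2 is 20 throughout. PLD is 30 at levels 0 to 3 and 20 at levels -1 and -2. In the Part 2 table, level -1 shows "1 dose level below the MTD" in the carfilzomib column and again in the PLD column.

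Sections 7.1.4, 7.2.5 and 7.3.4 use the same term drug by drug: five carfilzomib levels (20, 20/27, 20/36, 20/45, 20/56 mg/m²), two PLD levels (20, 30 mg/m²) and two dexamethasone levels (10, 20 mg).

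**The concern.** The reduction rules are safety instructions, and they rest on a term that the protocol uses in two ways without choosing between them. If the step down is null or does not exist, the rule cannot be carried out as written. Three things are at stake:

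- what a participant receives on resuming after a qualifying toxicity;
- whether a step that lowers no dose still counts towards the limits that stop a drug or all treatment;
- which regimen the Part 2 level -1 cohort receives. If Part 2 de-escalates, that cohort's regimen could become the phase II regimen.

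**Working it through.** No sample-size or power figure is involved. The figure to test is the maximum of two carfilzomib reductions, set against the doses that exist.

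**Inputs.** Paired doses from Section 5.2, taking carfilzomib as the dose from Day 8; per-drug lists from Sections 7.1.4, 7.2.5 and 7.3.4; limits from Section 6.2.1.

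**Readings.** Row reading: one level is one row down the Section 5.2 table, each drug counted from the assigned level. Per-drug reading: one level is the next lower listed dose of that drug. No re-escalation between episodes is assumed.

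| Level | Carfilzomib/PLD (mg/m²) | Rows: carfilzomib, two steps | Rows: PLD, one step | Per drug: lower carfilzomib doses | Per drug: lower PLD dose |
|---|---|---|---|---|---|
| 3 | 56/30 | 56→45→36 | 30→30 | 45, 36, 27, 20 | 20 |
| 2 | 45/30 | 45→36→27 | 30→30 | 36, 27, 20 | 20 |
| 1 | 36/30 | 36→27→27 | 30→30 | 27, 20 | 20 |
| 0 (start) | 27/30 | 27→27→20 | 30→20 | 20 | 20 |
| -1 | 27/20 | 27→20→none | 20→20 | 20 | none |
| -2 | 20/20 | none | none | none | none |

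**Carfilzomib from level 0.** By rows, the first step is null and the second is real. Per drug, the first is real and the second has no dose to go to. Either way there is one real reduction against two ordered and permitted.

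**Null steps, row reading only.** For carfilzomib, the step from level 0 to -1 changes nothing, which also empties the second reduction from level 1. For PLD, a step down changes nothing from levels 3, 2, 1 and -1, which is four of six levels. Only level 0 gives a fall, and level -2 has no row below it.

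**What remains on the per-drug reading.** There is no second carfilzomib step from level 0 or -1, none at all from -2, and no PLD step from -1 or -2. The PLD dose named for stomatitis is likewise no reduction at -1 or -2.

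**Dexamethasone.** Two reductions are permitted. From 20 mg the list offers one lower dose, 10 mg.

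**Part 2 level -1 (carfilzomib/PLD, mg/m²).**

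| Part 1 MTD | Row reading | Per-drug reading |
|---|---|---|
| Level 3 | 45/30 | 45/20 |
| Level 2 | 36/30 | 36/20 |
| Level 1 | 27/30 | 27/20 |
| Level 0 | 27/20 | 20/20 |

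The readings differ at every MTD from level 0 to 3.

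**The case against.** The strongest reply is that the per-drug lists settle the matter. The toxicity rules instruct each drug separately, which fits those lists better than paired rows, and on that reading every null step goes: level 0 carfilzomib moves from 27 to 20, and PLD moves from 30 to 20 at levels 0 to 3. This is a good argument for one reading. But Section 6.2 never points to the lists, and the only numbered levels are the paired rows. Nor do the lists supply a second carfilzomib step from level 0.

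A maximum of two is also only a cap, and a cap is not contradicted by having fewer steps available. That is fair for Section 6.2.1 alone. It does not cover Sections 6.2.2.1 to 6.2.2.3, which order the second step and stop therapy only at the third episode.

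Third, Section 6.2.1 lets the Principal Investigator depart from the rules in phase I Cycles 2 and later and in any phase II cycle. Most second episodes would fall there, so the practical effect is smaller. In phase I Cycle 1, however, the rules must be followed directly. The discretion also covers management of toxicity, not the definition of a cohort's regimen.

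Fourth, the MTD rests on Cycle 1 DLTs. Drug-attributed grade 4 cytopenias and febrile neutropenia of grade 3 or higher are DLTs whatever dose follows, and dosing is recorded on the case report forms. This stands: exposure can be reconstructed, and the DLT classification of those events is not at risk.

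Finally, the Part 2 entry could be read simply as the row below. It could, but it is written once under each drug, so the per-agent reading is equally open.

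**Conclusion.** The point holds, and it should be corrected. From the starting level, the two ordered carfilzomib reductions cannot both be real on either reading. This rests on the doses in Sections 5.2 and 7.1.4 being the only ones available and on no return to the previous dose between episodes, which Section 6.2.1 permits after one tolerated cycle. The Part 2 level -1 regimen is undefined between two alternatives for each MTD from level 0 to 3. Dexamethasone has one lower listed dose for two permitted reductions.

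Two stronger readings are not supported. A reader might infer that a level 0 participant is plainly to be re-treated at an unchanged carfilzomib dose after a first grade 4 cytopenia. That follows only on the row reading, with which the per-drug lists compete. A reader might also infer that everyone treated at level 0, or all of phase II if level 0 were the MTD, is bound to be affected. Only a participant with a triggering toxicity meets the reduction rule, and discretion limits its force after phase I Cycle 1 and throughout phase II.

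The sample size, the error rates and the response analysis are unaffected.

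**What to change.** Reconcile Sections 5.2, 6.2.1 to 6.2.3, 7.1.4, 7.2.5 and 7.3.4 through one per-agent table. It should state:

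- what each permitted reduction of carfilzomib, PLD and dexamethasone means from each starting level;
- what the Part 2 level -1 regimen is for each possible Part 1 MTD;
- where no lower dose exists, whether the step counts as a reduction and how the discontinuation limits then apply.

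The investigator sets all doses and clinical rules; none is proposed here. The cost is one table in an amendment, with no change to the sample size or the analysis.
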